2. Collection of baseline information including demographics, stage of prolapse, past medical history, past surgical history, history of past UTI, laboratory studies including collection of urine for urinalysis and bacterial gram stain and culture.
3. Computer-generated randomization of subjects to either the control group (standard non-latex foley catheter) or the treatment group (silver alloy-impregnated catheter), in blocks of 4.
4. Patients and study staff involved in outcome assessment will be blinded to type of treatment allocation.
4. Removal of catheter per standard post-operative catheter care (adequate urinary output over 24 hours, lack of gross hematuria, able to void voluntarily)
5. If a patient has symptoms of a UTI or seeks medical treatment for a UTI during the 6 week post-operative period, we will ask the patient to contact the study team.
6. Review of patient and medical records at 6 week follow-up visit for UTI and laboratory evidence, if available.
7. If suprapubic catheter still in place, sending urine sample obtained by catheter for urinalysis, bacterial gram stain and culture.

Biospecimen (types, number, volume, processing, storage): n/a

Plan for Dose Modification if Toxicity occurs (if applicable): n/a

Statistical Considerations

Endpoints

Primary: UTI rate

UTI is defined as:

- (1) any symptoms (fever $> 38^{\circ}\text{C}$, suprapubic tenderness, costovertebral angle tenderness, or otherwise unexplained systemic symptoms such as altered mental status, hypotension, or evidence of a systemic inflammatory response syndrome) requiring antibiotic treatment
- (2) urine culture with $> 10^5$ cfu / mL
- (3) urine culture with $> 10^3$ cfu/ mL and evidence of pyuria (dipstick positive for leukocyte esterase and/or nitrite, microscopic pyuria, or presence of microbes seen on Gram stain of unspun urine)²²

Secondary:

Power Statement:

Previous studies of transurethral latex catheters have demonstrated a reduction in CAUTI incidence of ranging from 27% to 73%¹²⁻¹⁵ with use of silver-impregnated catheters compared to standard latex foley catheters. Additionally, a previously published data from our center reported a CAUTI rate of 19%²³ with use of standard foley catheters used for SPC in a postoperative urogynecology population. Therefore, since there are no previous studies evaluating the CAUTI rate of silver-impregnated SPC use, a conservative estimate of 10% reduction will be used in our sample size calculation.

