To obtain 80% power, with a difference in UTI rate of 10%, then the sample size per group that we hope to recruit is 400. However, we anticipate 10% drop-out so we will plan to recruit 222 per group, summing 444 total participants.

Data Analysis:

Continuous variables will be compared using a two sided t-test with alpha ≤ 0.05 considered statistically significant. Binary outcomes (UTI vs. no UTI) will be compared using Fisher's exact test. Descriptive statistics will be used to describe continuous variables for the two types of catheters. Multiple logistic regression will be used to adjust for confounders such as prior UTI, duration of catheterization, type of surgery performed, age, BMI, and comorbid conditions. Strength of association between UTI rate and confounders will be assessed by calculating odds ratios and their corresponding 95% confidence intervals.

Human Safety Aspects

Risks: The literature review does not reveal any added adverse effects of using silver-alloy catheters, above standard non-silver-alloy coated catheters. Since all patients, regardless of study participation, will have SPCs placed post-operatively as part of routine care, we do not anticipate any additional risks to participants.

Individual Subject Stopping Rules (if applicable): n/a

DSMB (if applicable):

Members:

n/a

Charter:

n/a

Stopping Rules for Efficacy and Safety (if applicable):

n/a

Questionnaires that ask about Depression (if applicable)

Included in study? Yes No

If "Yes", state the plan of management for subjects with possible depression:

References

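### Fisher's exact test is valid but conservative for the UTI comparison: Boschloo's test would add about 2 points of power at no cost, and the catheter risk difference with its interval should be prespecified

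*Combined protocol and SAP*

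**What the plan says.** In Data Analysis, the comparison of UTI between catheters is a single sentence: "Binary outcomes (UTI vs. no UTI) will be compared using Fisher's exact test". The level and sidedness are written only for another test: "Continuous variables will be compared using a two sided t-test with alpha ≤ 0.05 considered statistically significant".

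The same section plans a multiple logistic regression adjusting for confounders, and adds: "Strength of association between UTI rate and confounders will be assessed by calculating odds ratios" with 95% confidence intervals. It does not say that catheter type is a term in that model, or that its odds ratio will be reported.

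The Power Statement takes its control rate from the centre's own data, which "reported a CAUTI rate of 19"%, and says "a conservative estimate of 10% reduction will be used in our sample size calculation". The sample size sentence begins "To obtain 80% power, with a difference in UTI rate of 10"%. It then says "the sample size per group that we hope to recruit is 400", followed by "we anticipate 10% drop-out so we will plan to recruit 222 per group, summing 444 total participants".

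**The concern.** There are two linked matters.

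- **The test.** Fisher's test conditions on the total number of events. The discreteness this brings makes its true type I error lower than the nominal level. That protection matters most when events are few. Here about 200 × 0.19 + 200 × 0.09 = 56 events are expected among 400 patients, so no cell is sparse. The unused type I error is lost power, and the power target has no margin to spare.
- **The estimate.** Aim 1 is to compare UTI rates, and the trial is sized on a difference in rates, yet the plan does not commit to estimating that difference. If the result is not significant, the p-value alone will not tell a reader whether the planned 10-point reduction has been excluded. An effect measure and interval chosen after the data are seen would not be prespecified.

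**Working it through.** **Inputs.** Control rate 19% (Power Statement). Effect 10%, read as 10 percentage points, so 19% v 9%. Power 80%. Recruitment of 222 per group with 10% drop-out. A two-sided 0.05 level, assumed to carry over from the t-test sentence.

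**Reading of the effect.** A 10% relative reduction would be 19% v 0.9 × 19% = 17.1%. That needs 6,431 per group, so it cannot be the basis of the plan.

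**Evaluable number.** 222 × 0.9 = 199.8, about 200 per group. The 400 per group in the text fits the other figures only as a total: 200 / 0.9 = 222.2.

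**The plan's own figure.** The usual normal approximation is

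n = [z₀.₉₇₅ √(2p̄(1−p̄)) + z₀.₈₀ √(p₁(1−p₁) + p₂(1−p₂))]² / (p₁−p₂)²

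With p̄ = 0.14:

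n = [1.960 × √0.2408 + 0.8416 × √0.2358]² / 0.01 = (0.9618 + 0.4087)² / 0.01 ≈ 188 per group.

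This formula does not describe Fisher's test, so power was computed exactly.

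**Exact power and size.** For each test, power = Σ Bin(x; 200, p₁) · Bin(y; 200, p₂), summed over every pair of event counts (x, y) at which the test rejects. Size is the same sum with p₁ = p₂. Boschloo's test uses Fisher's p-value as its statistic and sets the cut-off so that the largest size over all common rates is at most 5%. At 200 per group that cut-off is 0.0572. Since 0.0572 exceeds 0.05, every table that Fisher's test rejects is also rejected by Boschloo's.

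| Test, 200 per group | Power, 19% v 9% | Maximum size |
|---|---|---|
| Fisher | 79.4% | 4.0% |
| Boschloo | 81.3% | 4.96% |
| Fisher mid-p | 83.0% | 5.1% |
| Pearson chi-square | 83.3% | 5.1% |

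Fisher's size is 3.3% at a common rate of 9%, 3.6% at 14% and 3.7% at 19%. Its maximum of 4.0% occurs at a rate of 50%, far from the planned rates.

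**Gain over Fisher.** Boschloo: 81.3 − 79.4 = 1.9 points. Mid-p: 83.0 − 79.4 = 3.6. Chi-square: 83.3 − 79.4 = 3.9.

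**A table where the choice matters.** With 38/200 v 23/200, Fisher's p is 0.051, which is not significant. It lies below 0.0572, so Boschloo's test rejects. The Newcombe 95% interval for the difference is 0.4 to 14.6 points, which excludes zero.

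**What the interval adds.** Two non-significant results, with Newcombe 95% intervals:

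- 38/200 v 28/200: Fisher p = 0.23; difference 5.0 points (−2.3 to 12.3). The planned 10 points are not excluded.
- 28/200 v 28/200: Fisher p = 1; difference 0 (−6.9 to 6.9). The planned 10 points are excluded.

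The p-values alone do not separate these two cases with respect to the planned effect; the intervals do.

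**The case against.** The strongest reply is that Fisher's test controls type I error and delivers almost exactly what was promised. Power of 79.4% is 0.6 points below 80%. It passes 80% at 203 per group, which needs drop-out of (222 − 203)/222 = 8.6% or less instead of 10%. With no drop-out at all it is 83.8%. This stands: Fisher's test is an efficiency choice, and a reader who infers that it leaves the trial materially underpowered goes too far.

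Three other stronger readings are also unsupported.

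- **That Fisher costs 3.6 points outright.** That figure is the gap to mid-p, whose size can slightly exceed 5%. Against Boschloo, which keeps the size guarantee, the loss is about 2 points.
- **That the true target was 20% v 10%.** The pooled formula gives 199 per group for that pair, and Fisher's power there would be 76.8%. But the plan states 19% and gives no formula, so this is conjecture.
- **That the plan offers only a p-value, or that a null result could not be interpreted.** Adjusting for confounders implies an exposure of interest, so the logistic regression may well include catheter type, although the plan does not say so. Once arm counts are reported, anyone can compute the interval.

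The low end of the cited effect range does not argue for a different test either. At a 27% relative reduction (19% v 13.9%), Fisher's power is about 24% and chi-square's about 28%, so a non-significant result is likely under any of them. That bears only on the case for an interval.

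**Conclusion.** The point holds as a minor, free improvement. At 200 evaluable per arm and 19% v 9%, Fisher's true type I error is about 3.3% to 3.7% against a nominal 5%, and its power is 79.4%. Boschloo's test raises power to 81.3%, above the stated target, with no loss of type I error control and no extra patients. The missing estimate is a gap in specification: no catheter effect with an interval is named, and the odds ratios promised are those of confounders. It does not make the result uninterpretable.

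The conclusion assumes an absolute 10-point effect, 200 evaluable patients per group, and a two-sided 0.05 level for the UTI comparison. If 400 per group were truly meant, Fisher's power would be 98.1% and the choice of test would hardly matter; the case for a prespecified interval would remain.

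**What to change.** Replace the Fisher sentence in Data Analysis with one along these lines:

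> The proportion of patients with UTI will be compared between randomised groups by Boschloo's exact test, two-sided, at the 0.05 level; the primary estimate is the risk difference (standard minus silver-alloy) with a 95% Newcombe interval.

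A Miettinen-Nurminen interval would serve equally well. State that the test decides significance, since test and interval can disagree at the margin. Say also whether the logistic regression includes catheter type and reports its odds ratio.

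The cost is one or two sentences and no patients. Boschloo's test is less familiar, so the software should be named. If the sponsor prefers mid-p or chi-square, power rises by a further 1.7 to 2.0 points (83.0 or 83.3 less 81.3), and the price is a maximum size of about 5.1%. If Fisher's test is kept, the risk difference and interval should still be added.

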Aims:

- 1) To compare the UTI rate among women undergoing urogynecological procedures with a silver-alloy suprapubic catheter compared to the standard supra-pubic catheter.
- 2) To identify risk factors predisposing patients to suprapubic CAUTI.

Methods

Description of Recruitment Methods:

How will subjects be identified?

Individuals who are being scheduled for a surgery which routinely requires placement of suprapubic catheter intraoperatively (i.e. abdominal sacrocolpopexy, anterior vaginal colporrhaphy, Burch colposuspension with and without mid-urethral sling), will be approached about participating in the study in the pre-operative urogynecology clinic.

How will subjects be contacted?

Subjects will be contacted in the Urogynecology clinic during the pre-operative visit. They will also be contacted during their routine 6-week follow-up post-operative visit in Urogynecology clinic. Additionally, if a patient has symptoms of a UTI or seeks medical treatment for a UTI during the 6 week post-operative period, we will ask the patient to contact the study team.

Recruitment Materials (if applicable):

n/a

Subject Population:

Number (total, each subgroup) 444 total, 222 per group

Gender:

Male	0
Female	444

Ages: 18 to 99 years

Inclusion Criteria:

- patients requiring intra-operative placement of suprapubic catheters as part of routine post-operative care for repair of anterior compartment prolapse i.e. patients undergoing anterior colporrhaphy, Burch colposuspension, with or without mid-urethral sling

Exclusion Criteria:

- Known UTI at time of surgery

- Unable to provide informed consent
- Use of chronic intermittent self-catheterization pre-operatively
- Use of chronic prophylactic antibiotics
- Use of antibiotics for any indication other than UTI during peri-operative and 6-week post-operative period
- Presence of fistula involving urogenital tract
- Use of chronic steroids or immunosuppressant
- Immunocompromised patient

Step-by-Step Schedule (include all procedures, therapies – attach a table or flow chart if there are multiple procedures or visits and indicate the window of number of days in which the participant may return for follow-up visits):

1. Informed consent obtained pre-operatively to participate in study

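### Duration of catheterization is settled after randomisation and is not a confounder; leave it out of any adjusted silver versus standard odds ratio, and say which aim the logistic model serves.

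*Combined protocol and SAP*

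**What the plan says.** Data Analysis gives one regression model for UTI: "Multiple logistic regression will be used to adjust for confounders such as prior UTI, duration of catheterization", followed by type of surgery, age, BMI and comorbid conditions. The next sentence turns to the covariates themselves: "Strength of association between UTI rate and confounders will be assessed by calculating odds ratios". The unadjusted comparison is separate: "Binary outcomes (UTI vs. no UTI) will be compared using" Fisher's exact test.

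The Aims section has two entries. Aim 1 is the randomised comparison: "To compare the UTI rate among women undergoing urogynecological procedures with a silver-alloy suprapubic catheter" against the standard one. Aim 2 is to find risk factors for suprapubic catheter-associated UTI. The model is linked to neither, and catheter type is not named as a term in it.

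The Step-by-Step Schedule fixes the order of events. Step 3 is "Computer-generated randomization of subjects to either the control group" or the silver-alloy group. A later step is "Removal of catheter per standard post-operative catheter care (adequate urinary output over 24 hours, lack of gross hematuria, able to void voluntarily". UTI is followed over six weeks: "If a patient has symptoms of a UTI or seeks medical treatment for a UTI during the 6 week post-operative period", the patient is asked to contact the study team.

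**The concern.** A confounder of the catheter comparison would have to influence which catheter a woman receives. Randomisation decides that, and duration does not yet exist at that point. Prior UTI, age, BMI and comorbid conditions are baseline variables and may be adjusted for. Duration is of a different kind, for two reasons.

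- **It may be a mediator.** If catheter type changes how long the catheter stays in, part of any effect on UTI runs through duration, and adjustment removes that part. If an unmeasured risk factor also drives duration, adjustment can create an association where there is no effect.
- **It may be a consequence of the outcome.** UTI is counted over six weeks, so it can precede removal and may prolong catheterization.

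In either case the duration-adjusted odds ratio is not the effect of assignment. It could differ from the unadjusted result for a reason unrelated to baseline imbalance, and a reader would probably take the difference for a correction. Only this supporting estimate is at stake.

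**Working it through.** **Timing.** Randomisation is step 3 of the Step-by-Step Schedule. Removal is listed after it and depends on urinary output, hematuria and voiding after surgery. Duration is therefore a post-randomisation variable. This part needs no arithmetic.

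**Inputs from the plan.** The standard-arm rate is 19% and the difference 10%, read as percentage points, so 19% versus 9%. Recruitment is 222 per group with 10% drop-out: 222 × 0.9 = 199.8, about 200 evaluable per arm. (The Power Statement labels 400 as per group. It fits the other figures only as the total before drop-out, which is a separate point.)

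**Yardstick.** The planned odds ratio is (0.09/0.91)/(0.19/0.81) = 0.422. Its standard error on the log scale is

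√[1/(200 × 0.19 × 0.81) + 1/(200 × 0.09 × 0.91)] = √(0.0325 + 0.0611) = 0.306.

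**Assumed inputs.** The documents give no distribution of duration and no effect on it, so all of these are assumptions. Duration is log-normal with median 4.5 days and log-SD 0.5, and enters the model linearly. The window is 42 days. Silver acts only on the hazard while the catheter is in place. The results are large-sample logistic limits over 4,000 duration quantiles, so they carry no simulation error.

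- Pattern A: hazard 0.045 per catheter-day, none after removal. UTI is about 20% on standard.
- Pattern B: hazard 0.03 per catheter-day and 0.002 per day after removal. UTI is about 20% versus 13%.
- Silver hazard ratio in both patterns: 0.45 with no shift in duration, 0.47 with 5% shorter, 0.55 with 18% shorter, 0.45 where UTI adds days.

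The shift is ln(adjusted OR / unadjusted OR); the last column divides it by 0.306.

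| Pattern | Assumption about duration | Unadjusted OR | Duration-adjusted OR | Shift in log OR | Shift / SE |
|---|---|---|---|---|---|
| A | unaffected | 0.430 | 0.415 | −0.04 | −0.12 |
| A | silver 5% shorter | 0.427 | 0.434 | 0.02 | 0.05 |
| A | silver 18% shorter | 0.431 | 0.507 | 0.16 | 0.53 |
| A | UTI adds 4 days | 0.430 | 0.368 | −0.16 | −0.51 |
| B | unaffected | 0.608 | 0.604 | −0.01 | −0.02 |
| B | silver 5% shorter | 0.608 | 0.622 | 0.02 | 0.07 |
| B | silver 18% shorter | 0.617 | 0.684 | 0.10 | 0.34 |
| B | UTI adds 4 days | 0.608 | 0.629 | 0.03 | 0.11 |

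The last row adds days only to UTIs that arise while the catheter is in place. If every UTI adds four days, the adjusted figure is 0.585, on the other side of 0.608.

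**Check at the planned effect.** With inputs set to give 19% versus 9% (unadjusted 0.422), the adjusted odds ratio for no shift, 5% and 18% shorter is 0.407, 0.429 and 0.496 with no risk after removal. It is 0.419, 0.429 and 0.458 with 0.002 per day after removal.

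**Extreme cases.** A separate simulation of 1,000,000 patients per scenario gives 0.72 unadjusted and 1.00 adjusted when the whole effect runs through duration. It gives 1.00 and 1.25 when there is no effect but catheter type and an unmeasured risk factor both affect duration. These show what the mechanism can do; they are not forecasts for this trial.

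**Cost of leaving duration out.** If duration is affected by neither arm nor UTI, 4,000 simulated trials at 200 per arm give these shares with p < 0.05, duration omitted versus included: 0.823 versus 0.840 (A) and 0.446 versus 0.445 (B). The pattern B values reflect 20% versus 13% and are not the trial's planned power.

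**The case against.** The strongest reply is that the plan never names an adjusted catheter odds ratio. Aim 1 has Fisher's exact test, and the only odds ratios mentioned are those for the covariates, which is Aim 2 language. In a risk-factor model duration is a legitimate candidate. This stands as far as it goes: the text is ambiguous. But adjusting for confounders is the language of a treatment comparison, and an analyst following it could report a duration-adjusted catheter effect.

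The second reply is that no harm is shown. The removal criteria mention neither infection nor coating, patients are blinded, and an 18% shortening has no source in the documents. At 19% versus 9% with risk continuing after removal, even that shortening moves the odds ratio only from 0.422 to 0.458, a log shift of 0.08 or about a quarter of a standard error. This limits the expected size and is accepted. It does not turn duration into a baseline variable, and the documents do not say that those who decide on removal are blinded.

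The direction under pattern B when UTI prolongs catheterization also depends on which UTIs add days. That is correct, and it supports the view that the distortion cannot be predicted or corrected afterwards.

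**Conclusion.** The concern holds. Calling duration a confounder is wrong for any silver versus standard odds ratio; this follows from the order of events in the schedule and needs no assumption. The numerical consequence does rest on assumptions. It is negligible if neither catheter type nor UTI affects duration, and about one third to one half of a standard error if silver shortens duration by 18%. It reaches about half a standard error in the other direction if UTI adds four days and there is no risk after removal. The documents neither show nor exclude such effects. The fault is confined to a supporting adjusted analysis and should be corrected there.

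**What to change.** In Data Analysis, separate the two aims.

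- **Aim 1.** Estimate the adjusted silver versus standard odds ratio with catheter type and pre-randomisation covariates only: prior UTI, age, BMI, comorbid conditions and type of surgery as scheduled. Omit duration of catheterization. Scheduled surgery is the safe choice because the schedule does not state whether randomisation precedes the operation.
- **Aim 2.** Duration may be examined in a separate model labelled exploratory, with a note that UTI may occur before removal and may itself affect duration.

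Report duration by arm descriptively. The plan already provides for this: "Descriptive statistics will be used to describe continuous variables for the two types of catheters".

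The cost is about two sentences. No new data are needed: duration is already a planned covariate, and the scheduled operation is known at the pre-operative visit. The sample size, alpha and Fisher's exact test stay as they are.

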Other attempts to reduce CAUTI include the development of different types of catheters. Standard indwelling catheters are made from a variety of materials including polyvinyl chlorine, plastic, plain latex, polytetrafluoroethylene, silicone elastomer, pure silicone hydrogel and polymer hydromer⁸. More recently, specialized catheters have been developed which involve coating the inner, outer or both surfaces of the catheter with antimicrobial materials⁹. These materials can be antibiotic or antiseptic with the most common antiseptic material used being silver. Silver ions are bactericidal, are used safely when applied topically to humans and used in controlling infections¹⁰.

Previous studies of latex-based catheters have demonstrated that use of silver alloy impregnated catheters reduced the incidence of CAUTI.¹¹ The magnitude of this reduction has been reported to range from 27% to 73%¹²⁻¹⁵ in prospective randomized trials. These numbers are strengthened by a recent meta-analysis which concluded that silver alloy catheters significantly reduced bacteriuria by 3-fold compared with standard catheters¹⁶. Although the previous work demonstrates encouraging results in decreasing CAUTI, the studies have varied in patient population, clinical indication and definition of outcomes. Moreover, there are no previous studies evaluating the effectiveness of silver alloy impregnated catheters for suprapubic use.

Urogynecology patients undergoing pelvic reconstructive surgery require bladder drainage in the immediate post-operative period. This can be achieved by placement of either a transurethral or suprapubic catheter (SPC). Although the SPC is more invasive compared to a transurethral catheter, the SPC is used routinely in many gynecologic surgical practices because of its' many advantages. These include prevention of urethral trauma and stricture formation, decreased UTI¹⁷,¹⁸, increased patient satisfaction compared to chronic indwelling urethral catheters, less discomfort¹⁹, avoidance of urethritis²⁰, maintained ability to void spontaneously, easier nursing care²¹, and shorter hospital stay¹⁸. Review of literature does not demonstrate any benefit with any particular type of SPC²².

We hypothesize that this study will show a statistically significant decrease in UTI rate among the urogynecology patients undergoing suprapubic catheterization with a silver-alloy catheter compared to the standard catheter.

Schematic Design of the Study: randomized control trial

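### Data Analysis does not say whether Fisher's test or the adjusted logistic model decides Aim 1, and the adjusters include duration of catheterization, which is known only after randomisation

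*Combined protocol and SAP*

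**What the plan says.** Endpoints, under Statistical Considerations, names one primary endpoint: "Primary: UTI rate". The background predicts that "this study will show a statistically significant decrease in UTI rate", so success rests on a significance test.

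Data Analysis then gives three statements that bear on this endpoint:

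- An unadjusted test: "Binary outcomes (UTI vs. no UTI) will be compared using Fisher's exact test".
- An adjusted analysis: "Multiple logistic regression will be used to adjust for confounders such as prior UTI". Five further items are named after prior UTI: how long the catheter stays in, the operation done, age, body mass index and comorbidity.
- What that model is to report: "Strength of association between UTI rate and confounders will be assessed by calculating odds ratios and their corresponding 95% confidence intervals".

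No sentence calls either analysis primary, supportive or deciding. The Power Statement names no test. There is no rule for selecting or coding covariates, comorbid conditions are not defined, and the words *such as* leave the list open. Odds ratios are promised for the confounders; no effect estimate is specified for the catheter.

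Two other places matter. The second aim is "To identify risk factors predisposing patients to suprapubic CAUTI". Step 2 of the Step-by-Step Schedule lists the baseline data, including "past medical history, past surgical history, history of past UTI". Randomisation is step 3, and catheter removal comes later.

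**The concern.** An unadjusted comparison and a covariate-adjusted odds ratio are different quantities and can give different answers at the 0.05 line. If the plan does not say which one decides, the choice may be made after the data are seen, and nobody can later show that it was not driven by the result.

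The more serious part is the content of the covariate list. Randomisation makes the arms comparable on what was fixed beforehand. Duration of catheterization was not fixed beforehand: removal depends on urinary output, haematuria and voiding after surgery. If the catheter type affects duration, or if a UTI does, then conditioning on duration can remove part of the catheter effect or bias it. Calling the covariates confounders also invites adjustment for whatever looks imbalanced. In a randomised comparison, baseline covariates serve mainly to gain precision.

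At stake are a clear answer to Aim 1, the meaning of any adjusted catheter effect, and some power that the trial could have without extra patients.

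**Working it through.** **Inputs from the documents.** Control UTI rate 19% and a 10% reduction, read as 10 percentage points (19% v 9%); 80% power; 10% drop-out; 222 recruited per group. Two-sided 0.05 appears only in the t-test sentence and is assumed to apply throughout.

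**The plan's own figure.** 200 / (1 − 0.10) = 222.2, stated as 222. The 400 per group in the text therefore fits only as a total, that is 200 evaluable per arm. Taken literally, 400 per arm would give 98.4% power and about 445 recruits per arm. That conflict is a separate matter and must be reconciled.

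**Fisher alone, by exact enumeration.** Power = Σₓ Σᵧ Bin(x; 200, p₁) · Bin(y; 200, p₂) · 1[Fisher p ≤ 0.05].

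- p₁ = 0.19, p₂ = 0.09: 79.4%, close to the planned 80%.
- p₁ = p₂ = 0.19: type I error 3.7%.

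This does not prove that Fisher was the design test. The normal approximation gives 199 per arm for 20% v 10%, and 188 for 19% v 9%.

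**Uncorrected chi-square, same enumeration.** Power is 83.3% at 19% v 9%. Leaving Fisher is thus worth 83.3 − 79.4 = 3.9 points before any adjustment.

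**Fisher against a logistic model, by simulation.** The documents give no covariate strengths, so all are assumed. Both set-ups use 200 per arm.

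- *Set-up A* (4,000 trials per scenario): all six named covariates, with duration treated as if it were a baseline variable. Log odds ratios are zero; moderate (1.0 for prior UTI, 0.25 to 0.5 for the others); or doubled.
- *Set-up B* (8,000 trials per scenario): baseline covariates only (prior UTI, surgery type, age, BMI, comorbidities), with combined AUC from 0.65 to 0.73.

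| Set-up | Power: Fisher | Power: adjusted | Type I: Fisher | Type I: adjusted | Type I: either | Opposite sides of 0.05 at 19% v 9% |
|---|---|---|---|---|---|---|
| A, zero | 79.4% | 83.1% | 3.9% | 5.1% | 5.2% | 4.2% |
| A, moderate | 79.0% | 85.3% | 3.4% | 4.3% | 5.2% | 8.2% |
| A, doubled | 79.9% | 92.0% | 3.2% | 4.9% | 6.3% | 14.0% |
| B, weaker | 79.8% | 84.6% | 4.1% | 5.6% | 6.2% | 6.9% |
| B, stronger | 78.6% | 85.4% | 3.3% | 5.1% | 6.0% | 9.3% |

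Simulation error for a power near 80% is √(0.8 × 0.2 / 4,000) = 0.6 points in A and √(0.8 × 0.2 / 8,000) = 0.4 points in B.

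**Splitting the gain.** In set-up B the chi-square has 83.6% and 82.4% power. Adjustment itself adds 84.6 − 83.6 = 1.0 and 85.4 − 82.4 = 3.0 points. With covariates that predict nothing it adds none. Taking 0 to 4 points on top of about 83% to 84% gives about 83% to 88% for a baseline-adjusted model. The doubled row lies beyond this range. It assumes an odds ratio of exp(2) = 7.4 for prior UTI and includes duration, so I treat it as an extreme.

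**Events.** 200 × 0.19 + 200 × 0.09 = 38 + 18 = 56 expected UTIs, which limits the size of any model.

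**Timing of the covariates.** Set against the Step-by-Step Schedule: prior UTI is named in step 2, age falls under demographics, and comorbidity under medical history. BMI is not named there. Surgery performed is known only once the operation is done; planned surgery is known before. Duration ends at removal, after randomisation, and step 7 provides for a catheter still in place at a late stage, so a UTI can precede the end of catheterization.

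**The case against.** The best defence is that the plan already implies a division of labour. Fisher is the only test tied by name to UTI versus no UTI, and its exact power of 79.4% fits the design. The sentence after the logistic one reports associations of UTI with the confounders, not with the catheter, which matches Aim 2. In a risk-factor model, duration of catheterization is a legitimate candidate. One sentence naming Fisher as deciding would then close the gap and keep about 80% power.

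Much of this stands. Fisher is the likely implied test, and choosing it is a matter of method, not an error. But the hierarchy has to be inferred. The logistic model is said to adjust for confounders, and confounding has meaning only relative to an exposure, which here is the catheter. On that equally fair reading, duration enters a model for the catheter effect.

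A reader might infer more than the documents support:

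- *That the plan sets up two rival tests of the catheter.* It never says that the catheter term in the logistic model will be tested.
- *That the two results often disagree.* About 4% to 10% at the planned effect is not often. In set-up A under no effect it is 1.4%, 2.6% and 4.6%.
- *That false positives are seriously inflated.* Choosing between Fisher and one fixed model gives at most about 6%, because Fisher is conservative. Picking the best of Fisher and five covariate sets gives 6.0%, 6.4% and 9.2% in set-up A, but that presumes deliberate selection, which the plan does not describe. Error control is therefore no argument for adjustment over Fisher.

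**Conclusion.** The point holds in a limited form. Data Analysis does not name the analysis that decides Aim 1, leaves the covariate list open, and includes an adjuster known only after randomisation. The last is the firmest part: it follows from the order of steps in the protocol and needs no simulation, although the documents do not show whether the catheter in fact affects duration.

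The numerical stakes are modest. A fixed baseline-adjusted model would have about 83% to 88% power against 79.4% for Fisher, with type I error of about 4% to 5.5% against 3.7%. Roughly 4 points of that gain come from leaving a conservative test, and about 0 to 4 from adjustment. These figures rest on 200 evaluable per arm, 19% v 9%, two-sided 0.05 and assumed covariate strengths. The trial is not invalid as planned, but its headline conclusion could turn on a choice that has not been made, and the remedy is cheap.

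**What to change.** Before any unblinded data are seen, amend Data Analysis as follows.

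- **Aim 1, confirmatory.** A logistic model of UTI on randomised catheter, analysed as randomised, with a short fixed list of covariates recorded before randomisation: prior UTI, planned surgery type, age, BMI (once its recording at baseline is confirmed) and one comorbidity count. Test the catheter term at two-sided 0.05 and report the model-standardised risk difference with its 95% confidence interval. Exclude duration of catheterization.
- **Sensitivity.** Keep Fisher's test, and state that it neither rescues nor overturns the confirmatory result.
- **Covariate rule.** Do not choose covariates from observed imbalance or p-values.
- **Aim 2, exploratory.** Keep a separate logistic model for risk factors, where duration may be included. Replacing both present sentences with the Aim 1 model alone would leave Aim 2 without an analysis.

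The cost is wording, a check that BMI is recorded at baseline, and slightly more modelling; no patients or visits are added. Fisher loses any confirmatory role, and the model must stay small because only about 56 events are expected. If the sponsor prefers Fisher as the deciding test, saying so, closing the list and keeping duration out of any adjusted catheter comparison would remove the ambiguity, but forgo the power gain.
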